11.2 Determination of Sample Size

Primary outcome:

Sample size calculation of the ESTxENDS trial at 6 months follow-up: Based on the results of a systematic review and meta-analysis of previous trials, we expect an RR of smoking cessation of 1.6. Based on our previous RCTs, we expect a 12% quit rate in the control group and a 19% quit rate in the intervention group (ENDS + SOC) (7% absolute difference in continuous abstinence rate from target quit date [TQD]) for the main outcome in ESTxENDS at 6 months. With a two-sided alpha of 0.05 and a power of 90%, we therefore planned to include a minimum 557 smokers per group, for a total of 1,114 smokers, to find a significant difference in quit rates. Previous experience suggests we should assume a 5% loss to follow-up, so we increased our sample size by 5% (59 smokers). We will thus recruit 1,172 smokers. Though participants in the control group will not be actively provided with ENDS and asked not to use ENDS during the first 6 months of the study, we expect that 5% will still purchase ENDS on their own. The sample size of the entire trial is based on the primary outcome; the power to find a statistically significant difference for secondary outcomes is limited to the total number of participants.

Estimated power to detect significant differences in groups on smoking cessation at 12- and 24-months follow-up: Assuming 10% will have quit smoking in the control group at 12 months (continuous smoking cessation rate from TQD), and applying the RR of 1.6, we estimate 16% will have quit in the intervention group. Assuming 7% loss to follow-up, we will have 86% power to detect such a difference. Based on the literature and previous experience in our own trials,^{133, 163} we expect a 10% relative increase in absolute smoking cessation rate by choosing 7-days point prevalence as the main outcome with no change in RR estimate.¹⁶³ We will have 90% power to detect a significant difference by choosing the 7-days point prevalence as a main outcome for the 12-months follow-up. We thus expect an 11% quit rate in the control group and 17% in the intervention group at the 12-month follow-up (6% absolute difference). At the 24-month follow-up, we can expect 8% in the control group will have stopped smoking and 12% in the intervention group. Assuming a 10% loss to follow-up rate, we will have 62% power to detect a significant difference between groups.

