4.1 Confidence intervals and *P* values

All applicable statistical tests will be 2-sided and will be performed using a 5% significance level. Estimates and effect measures will be presented with a two-sided 95% confidence interval.

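### Protocol 11.2 prints 11% v 17% where its unchanged RR of 1.6 gives 17.6%, and its 86%, 90% and 62% power figures leave out the losses it cites

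*Supplement*

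**What the plan says.** Everything here stands in the second paragraph on the primary outcome in Protocol 9.0, section 11.2.

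- **Continuous abstinence, 12 months.** The control rate is given as "Assuming 10% will have quit smoking in the control group at 12 months (continuous smoking cessation rate from TQD"), followed by "applying the RR of 1.6, we estimate 16% will have quit in the intervention group". Then: "Assuming 7% loss to follow-up, we will have 86% power to detect such a difference".
- **7-day point prevalence, 12 months.** The rates are derived by a rule: "we expect a 10% relative increase in absolute smoking cessation rate by choosing 7-days point prevalence as the main outcome with no change in RR". The power claim is "We will have 90% power to detect a significant difference by choosing the 7-days point prevalence as a main outcome for the 12-months follow-up", and the rates are printed as "We thus expect an 11% quit rate in the control group and 17% in the intervention group at the 12-month follow-up (6% absolute difference").
- **24 months.** "At the 24-month follow-up, we can expect 8% in the control group will have stopped smoking and 12% in the intervention group", with 10% loss and 62% power.

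Section 5.1 makes validated 7-day point prevalence the primary outcome at 12 and 24 months. Section 6.1 gives 586 per group. Section 11.5 counts participants lost to follow-up as smokers in the intention-to-treat analysis. SAP 2.0, section 4.1, sets the error rate: "All applicable statistical tests will be 2-sided and will be performed using a 5% significance level".

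**The concern.** Two things in the paragraph do not fit together. The rule for 7-day prevalence leaves the relative risk at 1.6, but 17% over 11% is 1.55; the printed difference of 6 points is likewise not the 6.6 that the rule yields. And the paragraph announces losses of 7% and 10%, which should pull power below the figure for the full 586 per arm, yet the stated figures look like full-sample figures.

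At stake is the stated chance of detecting the assumed effect on a primary outcome. A reader who takes the printed rates and the stated loss cannot arrive at 90%. The paragraph also sets 86% and 90% side by side when comparing the two outcome definitions, so both figures should rest on the same footing and on rates the paragraph actually supports.

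**Working it through.** **Inputs.** Two-sided 5% (SAP 4.1); 586 per arm (Protocol 6.1); 7% loss at 12 months and 10% at 24 months (Protocol 11.2). The two-group chi-square test is the one that SAP 6.3.1 gives for the 6-month outcome; its use at 12 and 24 months is my assumption, since the SAP excludes those time points.

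**Rates.** Continuous abstinence: 10% and 10% × 1.6 = 16%. Seven-day prevalence by the rule: 10% × 1.1 = 11% and 11% × 1.6 = 17.6%. As printed: 11% and 17%. At 24 months: 8% and 12%.

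**Formula.** With p̄ = (p₁ + p₂)/2 and n per arm,

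power = Φ{ [ (p₂ − p₁) − 1.96·√(2p̄(1 − p̄)/n) ] / √([p₁(1 − p₁) + p₂(1 − p₂)]/n) }.

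**Step 1: reproduce the stated figures (n = 586, no loss).**

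- 10% v 16%: (0.06 − 1.96 × 0.01965)/0.01957 = 1.098, power 86.4% (stated 86%).
- 11% v 17.6%: (0.066 − 1.96 × 0.02045)/0.02036 = 1.273, power 89.8% (stated 90%).
- 8% v 12%: (0.04 − 1.96 × 0.01753)/0.01749 = 0.323, power 62.7% (stated 62%).
- 11% v 17%, as printed: (0.06 − 1.96 × 0.02027)/0.02020 = 1.004, power 84.2%, not 90%.

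So 90% comes from RR 1.6 with nobody lost. For 11% v 17%, the unpooled, arcsine, continuity-corrected, log-RR and exact chi-square versions give 79% to 85% across 545 and 586 per arm; none reaches 90% two-sided.

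**Step 2: apply the losses, in two ways.** (a) Analyse only those followed: 586 × 0.93 = 545 at 12 months, 586 × 0.90 = 527 at 24 months. (b) Keep 586 and count the lost as smokers, as section 11.5 does, so the rates are multiplied by 0.93 or 0.90.

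| Comparison | No loss | (a) followed only | (b) lost = smokers | Rates in (b) | Stated |
|---|---|---|---|---|---|
| 12 mo continuous, 10% v 16% | 86.4% | 83.9% | 83.5% | 9.30% v 14.88% | 86% |
| 12 mo 7-day, RR 1.6, 11% v 17.6% | 89.8% | 87.6% | 87.3% | 10.23% v 16.37% | 90% |
| 12 mo 7-day, printed, 11% v 17% | 84.2% | 81.5% | 81.1% | 10.23% v 15.81% | 90% |
| 24 mo, 8% v 12% | 62.7% | 58.1% | 57.7% | 7.20% v 10.80% | 62% |

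Exact enumeration of the chi-square test at 545 per arm agrees: 84.1%, 87.9% and 81.8% for the three 12-month rows.

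**The case against.** The strongest reply is that 17% is a slip in print, not the working assumption. The rule gives 17.6%, and 17.6% with 586 per arm returns the stated 90%. That stands, and it limits the point. A reader might infer that power for the 12-month primary is simply 82%, that point prevalence is weaker than continuous abstinence, and that a switch between the two was justified by a gain that does not exist. The documents do not support this. The reversal (about 82% against 84%) needs the printed 17% and has to disregard the unchanged RR in the same paragraph. At RR 1.6 point prevalence keeps an advantage of three to four points, with loss (87.6% against 83.9%) or without (89.8% against 86.4%). Nor does any version shown make continuous abstinence the 12-month primary: Protocol 2.0 has no 12-month visit, and the change history ties the extension in version 7.0 to new funding. The paragraph compares two candidate definitions; it records no replacement.

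Two other defences are weaker. The sentence with the 90% does not itself repeat the 7%, and 11% v 18% with 545 per arm would give 90.8%. But 18% is printed nowhere, and the neighbouring 86% and 62% match 586 per arm although each is tied to a stated loss. It might also be said that the rates already count lost participants as smokers. Table 11.2-1 speaks against that: its 12-month quitters, 49 + 38 = 87 and 11 + 44 = 55, are 16% and 10% of 545, the number left after 41 per arm are lost.

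It is also true that little depends on these figures. The sample size was set by the 6-month outcome, and the SAP does not cover 12 or 24 months.

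**Conclusion.** The point holds as an internal inconsistency with a modest overstatement of power. The printed 11% v 17% contradicts the RR of 1.6 kept in the same paragraph, and the 86%, 90% and 62% are no-loss figures given alongside stated losses. On the plan's own assumptions they should read about 84%, 87–88% and 58%. At RR 1.6 the chance of missing the assumed 12-month effect is 12–13%, not 10%. Only if 17% is truly intended does it rise to about 18–19%, and only then does the power advantage of point prevalence disappear.

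This rests on a two-sided 5% chi-square test with equal arms, on equal loss in both arms, and on the rates applying to participants who are followed, as Table 11.2-1 indicates for 12 months. That the losses were left out is inferred from three figures that all match 586 per arm; the protocol does not show its calculation. No relative risk is given for 24 months, so only the unapplied loss is at issue there.

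**What to change.** In section 11.2, first decide which 12-month intervention rate is meant.

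- **If RR 1.6:** replace 17% by 17.6% and the 6-point difference by 6.6 points, and state power of about 87%. The statement that point prevalence raises power can stay.
- **If 17%:** remove the claim that the RR is unchanged, state power of about 81%, and drop the claimed gain in power.

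In either case, apply the 7% and 10% losses by counting lost participants as smokers, as section 11.5 does. Restate continuous abstinence at 12 months as about 84% (83.5% on that rule) and the 24-month figure as about 58%. Add one sentence saying how loss enters the calculation.

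The cost is an edit to protocol text and slightly less favourable stated figures. Sample size and the 6-month analysis are untouched.

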6. STUDY DESIGN

6.1 General study design and justification of design

The ESTxENDS trial is a multicentre, pragmatic, open-label randomized controlled trial with two parallel groups allocated in a 1:1 ratio. The trial will be based on a superiority hypothesis of ENDS + SOC for smoking cessation to SOC alone in adult (≥ 18 years) smokers. The intervention group will receive ENDS and nicotine-containing e-liquids to use *ad libitum* until 6 months visit, plus SOC. The control group will receive SOC only. At the baseline visit, participants in the control group will receive a voucher ("BERNcity Geschenkkard" or similar voucher for Lausanne, Geneva, Zürich and St. Gallen) worth CHF50. The amount of CHF50 is of similar monetary value to what the intervention group will receive in form of the two ENDS devices and the e-liquids. A total of 1172 smokers will be randomized in the study, 586 in each group. Recruitment of the participants is planned to occur over 13-18 months at all 5 study sites. Our main outcome at the 6-month visit will be self-reported continuous smoking cessation after target quit date, with blinded biochemical verification by exhaled carbon monoxide (CO), urinary cotinine, anabasine, VOCs, TSNA (NNN, NNK and its metabolite NNAL) and PAHs (1- and 2-Naphtol and 1-OHP) levels. At the 12-month and 24-month visit, the main outcome will be the self-reported 7-day point prevalence abstinence (not having smoked cigarettes within the preceding week), again all confirmed by the exhaled CO level and the urinary level of cotinine and anabasine. Statisticians and laboratory personnel will be blinded to group allocation. Participants and clinicians will not be blinded. We will use the methodology of a clinical trial investigating a medicinal product to test the efficacy and safety of ENDS.

Figure 6.1-1: ESTxENDS trial design schematic

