Secondary outcomes: The sample size of the entire trial is based on the primary outcome; the power to find a statistically significant difference for secondary outcome is limited to the total number of participants. For safety outcomes, we do not expect to find statistically different results between groups on SAEs. For toxicological outcomes of ENDS, such as measures of urinary biomarkers, we will compare participants based on ENDS exposure. Table 11.2-1 presents the number of participants we expect to fall into each category of ENDS and cigarette smoking over follow-up. In the intervention group, we expect that 19% of smokers would quit and 30% would use of ENDS at the 6-month follow-up.⁹ In the control group, we expect that 12% of smokers who quit at 6-month follow-up. Though participants in the control group will not be actively provided with ENDS during the first 6 months of the study, we expect 5% will purchase ENDS on their own.

Table 11.2-1: Expected distribution of participants over follow-up

Group	Intervention group					Control group					Legend:
	Ai	Bi	Ci	Di	Ei	Ac	Bc	Cc	Dc	Ec	
ENDS	+	+	-	-		+	+	-	-		Ai= ENDS use, stop smoking, intervention
Tob smk	-	+	-	+		-	+	-	+		Bi= ENDS use, smoking, intervention
Baseline		586							586		Ci= No ENDS, stop smoking, intervention
											Di= No ENDS, smoking, intervention
											Ei= Lost to follow-up (LTFU), intervention
6 months: N	56	111	50	340	29	11	17	56	473	29	Ac= ENDS use, stop smoking, control
% of group	10%	20%	9%	61%	5%	2%	3%	10%	85%	5%	Bc= ENDS use, smoking, control
12 months: N	49	93	38	365	41	11	16	44	474	41	Cc= No ENDS, stop smoking, control
% of group	9%	17%	7%	67%	7%	2%	3%	8%	87%	7%	Dc= No ENDS, smoking, control
24 months: N	37	79	32	380	59	11	16	26	475	59	Ec= LTFU, control
% of group	7%	15%	6%	72%	10%	2%	3%	5%	90%	10%	

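### Protocol 9.0 section 11.2 gives two incompatible 24-month expectations: 8% v 12% in the power sentence, about 7% v 13% in Table 11.2-1

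*Supplement*

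**What the plan says.** Section 11.2 of protocol 9.0 sizes the trial on the 6-month outcome and then gives estimated power for the 12- and 24-month follow-ups.

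- **Effect assumption for the section:** "we expect an RR of smoking cessation of 1.6".
- **24-month rates:** "At the 24-month follow-up, we can expect 8% in the control group will have stopped smoking and 12% in the intervention group".
- **24-month power:** "Assuming a 10% loss to follow-up rate, we will have 62% power to detect a significant difference between groups".
- **Point prevalence against continuous abstinence:** the 12-month paragraph expects a "10% relative increase in absolute smoking cessation rate by choosing 7-days point prevalence as the main outcome with no change in RR estimate".

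Further down the section, under secondary outcomes, Table 11.2-1 projects how many participants fall into each category of ENDS use and smoking. Its 24-month counts are "24 months: N 37 79 32 380 59 11 16 26 475 59", and the percentages beneath begin "of group 7% 15% 6% 72% 10% 2% 3% 5% 90% 10". In each arm the cells run: ENDS and quit, ENDS and smoking, no ENDS and quit, no ENDS and smoking, lost to follow-up.

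Section 5.1 makes 7-day point prevalence abstinence the primary outcome of the 12- and 24-month follow-ups. Section 11.5 counts participants lost to follow-up as smokers.

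**The concern.** The quitter cells of the 24-month row do not add up to the rates in the power sentence. The table expects fewer control quitters and more intervention quitters, so both differences widen the effect. The 6- and 12-month rows do agree with rates printed in the text, so the reader expects the 24-month row to do the same.

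Section 11.2 is the only place where 24-month power is planned, because the SAP leaves the 12- and 24-month outcomes out. Someone reading a 24-month result against the plan would therefore find two expected effects and one power figure. The table also sets the expected group sizes for the comparisons by ENDS exposure, so a wrong row would carry over to those.

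**Working it through.** **Inputs.** Two-sided alpha 0.05 (section 11.2); 586 randomised per arm (section 6.1); 10% loss at 24 months, shown as 59 lost per arm in the table; rates as quoted above.

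**Rates implied by the table at 24 months**

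- Intervention quitters: 37 + 32 = 69. Followed: 37 + 79 + 32 + 380 = 528. Rate 69/528 = 13.1% (printed 7% + 6%).
- Control quitters: 11 + 26 = 37. Followed: 11 + 16 + 26 + 475 = 528. Rate 37/528 = 7.0% (printed 2% + 5%).
- RR 69/37 = 1.86; difference 6 points. The sentence gives RR 12/8 = 1.5; difference 4 points.

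**The other rows**

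- 6 months: (56 + 50)/557 = 19.0% and (11 + 56)/557 = 12.0%. The text has 19% v 12%.
- 12 months: (49 + 38)/545 = 16.0% and (11 + 44)/545 = 10.1%. The text has 16% v 10% for continuous abstinence; its point-prevalence rates are 17% v 11%.

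**Power formula.** With n per arm, p̄ the mean of the two rates and d their difference:

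power = Φ{ [d − 1.96·√(2p̄(1−p̄)/n)] / √[(p₁(1−p₁) + p₂(1−p₂))/n] }

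**The plan's own figure, 8% v 12%**

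- n = 586: null SE √(0.18/586) = 0.01753, alternative SE √(0.1792/586) = 0.01749. (0.04 − 0.03435)/0.01749 = 0.323, so power is 62.7%. This reproduces the stated 62%.
- n = 528: null SE 0.01846, alternative SE 0.01842. (0.04 − 0.03619)/0.01842 = 0.207, so power is 58.2%. This does not. Exact power of the chi-square test is 62.9% and 58.5% respectively.

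**The table's rates, 7% v 13%**

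- n = 528: p̄ is again 0.10, so the null SE is the same; alternative SE √(0.1782/528) = 0.01837. (0.06 − 0.03619)/0.01837 = 1.296, so power is 90.3% (90.7% from the counts 37 and 69).
- n = 586: (0.06 − 0.03435)/0.01744 = 1.471, so power is 92.9%.

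| 24-month rates | Source | 528 per arm | 586 per arm |
|---|---|---|---|
| 8% v 12% | power sentence | 58% | 63% |
| 8% v 12.8% | 8% × RR 1.6 | 72% | 77% |
| 7% v 13% | Table 11.2-1 | 90% | 93% |

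**Readings that might reconcile the two**

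- *All randomised as denominator.* 69/586 = 11.8% is close to 12%, but 37/586 = 6.3% is further from 8%. Power is still 90.4%.
- *Table continuous, sentence point prevalence.* The plan's 10% uplift gives 7.0% × 1.1 = 7.7% and 13.1% × 1.1 = 14.4%, not 8% v 12%. Point prevalence of 12% also cannot lie below continuous abstinence of 13%.
- *The reverse.* The control arm then has 7% point prevalence against 8% continuous abstinence, which fails in the same way.

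**The case against.** The strongest reply is rounding. The counts look like whole percentages multiplied by the number followed: 0.07 × 527.4 = 36.9, printed as 37. Reporting 13.1% v 7.0% and 90.7% power then claims more precision than the table has. If each printed percentage may be off by half a point, 7.9% v 12.1% is just possible, and at 527 per arm that gives 62.3%, the stated power with the loss deducted. The warning about precision stands, and about 7% v 13% and about 90% are as fine as the table allows. The rescue does not. Its control rate needs about 2.45% × 528 = 13 and 5.45% × 528 = 29 quitters, where the table prints 11 and 26, and every cell must sit near the edge of its rounding range in the favourable direction.

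It is also fair that the power sentence does not cite the table, which serves the exposure comparisons, and that the 12-month row matches only the continuous-abstinence rates. The table therefore does not show which 24-month figure is mistaken. The plan also nowhere says that RR 1.6 must hold at 24 months.

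Three stronger inferences are not supported:

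- **That 62% is a miscalculation.** It is right for 8% v 12% at 586 per arm. Using all 586 is consistent with counting lost participants as smokers if 8% and 12% are rates over everyone randomised. The plan does not say so, and its sentence invokes the 10% loss.
- **That row totals of 587 are an error.** One participant over 586 is ordinary rounding across five cells.
- **That a non-significant 24-month result could not be interpreted.** It can be read from its estimate and confidence interval. What is missing is a single planned benchmark.

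**Conclusion.** The inconsistency stands. Section 11.2 expects 8% v 12% in one place and about 7% v 13% in another for the same follow-up, and no choice of denominator or abstinence definition reconciles them. The implied power differs by about 30 points on either basis: 58% v 90% at 527-528 per arm, or 63% v 93% at 586. These figures assume two-sided alpha 0.05, equal arms, a normal-approximation test of two proportions, and table percentages taken as printed.

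The documents do not show which set was intended. The scope is narrow: the trial's size rests on the 6-month outcome, and the 6-month rates, table row and analysis are untouched. The point deserves correction because the 24-month outcome is labelled primary for its follow-up.

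**What to change.** Choose one set of 24-month rates. State whether they are point prevalence or continuous abstinence, and whether the denominator is participants followed or all randomised. Use the set in both the sentence and the table row.

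- If 8% v 12% among those followed is intended, the row should show about 42 control and 63 intervention quitters of 527 (0.08 × 527 = 42.2; 0.12 × 527 = 63.2).
- If RR 1.6 is meant to hold, the rates are 8% v 12.8%.
- If the table is right, the sentence should read about 7% v 13%.

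Then restate the 24-month power from the chosen rates, with the 10% loss handled as the text says: about 58%, 72% or 90% respectively at 527-528 per arm. If the rates are over all randomised, say so and keep 586.

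The cost is one sentence or one table row and a restated figure. Sample size, visits and tests do not change.

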3. BACKGROUND AND RATIONALE

3.1 Background and Rationale

Research questions

- 1) How effective are ENDS in helping smokers quit, and reducing the number of cigarettes per day smoked over 6, 12 and 24 months of follow-up?
- 2) Do ENDS result in adverse events when smokers use them as quitting aids?
- 3) Does using ENDS effectively reduce exposure to inhaled toxic compounds?
- 4) Does using ENDS improve health-related clinical outcomes (respiratory symptoms) and surrogate outcomes (oxidative stress, cardiovascular risk factors)?

Background

Smoking is the leading cause of avoidable death worldwide, is one of the top five causes of morbidity and lowered disability-adjusted life-years.² Cigarette smoking eventually kills one in two smokers, mostly through cancer, heart disease and respiratory failure.³ More than a quarter of the Swiss population still smokes cigarettes.⁴

ENDS are electrically-driven devices that reproduce many features of tobacco cigarettes such as release of smoke (aerosol for ENDS), mimic the gesture of smoking and provoke similar mouth experiences such as the “throat hit”, typical of cigarette smoking.⁵ They consist of a battery part, a liquid storage tank, and an atomizer that aerosolizes the liquid by generating heat to a resistance.⁶ The liquid consists of propylene glycol, glycerol, distilled water, flavorings, ethanol and nicotine. Consumers (commonly called ‘vapers’) may choose from several types of ENDS, nicotine strengths, and a long and growing list of flavors. Compared to traditionally used nicotine replacement therapies such as nicotine patches, gums, sprays, lozenges and inhalers, ENDS may have different effects, since they better replicate the experience of traditional cigarette smoking and more quickly deliver nicotine to the blood.

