4.3 Secondary Objectives

Secondary objectives are to assess the effect of using ENDS on exposure to inhaled toxic compounds and assess the effect of ENDS use on health-related outcomes, including clinical health-related outcomes (respiratory symptoms, pulmonary function,, olfactory function, inflammatory biomarkers) and surrogate health-related outcomes (oxidative stress, cardiovascular risk factors, micronuclei in mouth epithelium).

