For measures of carcinogenicity, such as measures of incomplete combustion agents (VOCs and PAH: 1-OHP, 1- and 2-NAPH in urine)^{29,30} and exposure to TNSAs (NNK and NNN in urine),¹⁸ and measures of oxidative stress in urine (8-OHdG and 8-isoprostane),^{41, 91, 164} and MN in buccal epithelium, we will compare groups that stopped smoking with or without ENDS in intention to treat analyses (Ai+Ci vs. Ac+Cc; 112 vs. 70) and in per protocol analyses (Ai+Ac vs. Ci+Cc; 65 vs. 117). Based on previous cross sectional studies contrasting past smokers to smokers,^{52, 164, 165} we estimate a 48% power to detect significant differences between quitters and continuing smokers for 8-OHdG and 100% for 8-isoprostane between baseline and follow-up, at alpha 0.05 and an assumed correlation between baseline and follow-up of 0.7 (Table 11.2-2). We will perform 3 determinations of buccal MN on 2000 cells for each participant. Based on published results,^{99, 100, 166-168} we expect a baseline frequency among non-smokers of 0.74 MNs per thousand cells and a between-subject GSD of 1.3. We will have 80% power to detect a significant difference between smokers and non-smokers for a frequency ratio (FR) of 1.5.

For the 6-months changes in cardiovascular risk factors, we do not have direct data from RCT of ENDS use. Using data from previous RCT on nicotine replacement therapy, we expect a mean increase in HDL-cholesterol of 0.107 mmol/l (95% confidence interval 0.057 to 0.158 mmol/l) among quitters,⁵⁴ an increase in systolic blood pressure of 1.65 mm Hg and in diastolic blood pressure of 0.90 mm Hg after 6 months in quitters.^{55, 56} Considering data from the CoLaus study, a study on cardiovascular risk factors in a random sample of the Lausanne population, we expect to only have a 10 to 40% chance to detect a difference between ENDS users and continuing smokers.¹⁶⁹ We expect to be able to have 100% power to detect changes in respiratory symptoms.^{8, 170}

We do not expect to have adequate power to detect changes in incidence of cancer. However, we will apply strict open access rules and post the data on rigorous and systematic assessment of self-reported cancer in an online repository to enable the international community to pool results with other datasets and answer more definite answers on these important outcomes

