11.4.1 Datasets to be analysed, analysis populations

All analyses will be done on the intention-to-treat principle set whereby all randomized patients will be analyzed in the allocated group. This means regardless of any protocol violations such as participants in the control group purchasing an ENDS on their own or early treatment discontinuations in the intervention group.

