11.4.3 Secondary Analyses

We will repeat the calculations described in 11.4.2 for the secondary smoking cessation outcomes. To test the effect of ENDS on reducing the number of cigarettes smoked per day, we will define a binary predictor of >50% smoking reduction from baseline to follow-up smoking and repeat the analyses for the main outcome of quitting. We will also use joint multivariate random-effects (JMRE) models allowing to model CPD and smoking cessation. In addition, we will use mixed linear effect model to analyze the change in CPD modelled as a continuous outcomes over time.

We will present modified per-protocol sensitivity analyses, in particular for participants in the control group who might have started using ENDS in the first six months.

For the measures of changes in measures of urinary biomarkers, exhaled breath measures, CVRFs and respiratory symptoms and pulmonary function from baseline to the 6-months visit, we will first compare the changes in these measures between the intervention and control group using two-sample t-tests or Wilcoxon rank-sum test, whenever appropriate. We will then fit univariate and multivariate mixed linear effect models. We will use multivariate linear and multinomial logistic regression models to compare groups according to their exposure to tobacco smoking and ENDS.

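### Protocol 11.2 labels a quitters-only biomarker contrast intention-to-treat, contrary to 11.4.1 and to the whole-arm comparison in 11.4.3

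*Supplement*

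**What the plan says.** Section 4.3 sets the aim: "Secondary objectives are to assess the effect of using ENDS on exposure to inhaled toxic compounds". Research question 3 in section 3.1 puts it as "Does using ENDS effectively reduce exposure to inhaled toxic compounds".

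Three places in protocol 9.0 bear on how this is analysed.

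- Section 11.2, secondary outcomes: "we will compare groups that stopped smoking with or without ENDS in intention to treat analyses (Ai+Ci vs. Ac+Cc; 112 vs. 70"). The same sentence adds a second contrast, "in per protocol analyses (Ai+Ac vs. Ci+Cc; 65 vs. 117"). In the legend to Table 11.2-1, A and C are the stopped-smoking cells, with and without ENDS use; i and c mark the arm.
- Section 11.4.1: "All analyses will be done on the intention-to-treat principle set whereby all randomized patients will be analyzed in the allocated group".
- Section 11.4.3, on six-month change in a list of measures that includes the urinary biomarkers: "we will first compare the changes in these measures between the intervention and control group". Mixed models follow, then models by smoking and ENDS exposure. The synopsis repeats the arm comparison. Micronuclei are not in the 11.4.3 list.

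SAP 2.0 lists toxic exposure among its objectives (1.2), but its core secondary outcomes (6.1) leave out the toxicology panel. NNAL and anabasine appear in Table 3 only as dichotomised values. Section 6.7 places further outcomes and subprojects outside the SAP. Of the documents shown, the protocol alone says how the panel is to be compared.

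**The concern.** The same protocol uses one label for two different populations. Under 11.4.1, an intention-to-treat comparison keeps everyone as allocated. Under 11.2 it keeps only those who quit, a group formed after randomisation by the outcome the intervention is meant to change.

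Two consequences follow. First, the quitters in the two arms need not be alike at baseline: the additional people who quit because they were given ENDS may differ from those who would have quit with standard care, for example in dependence or prior exposure. Second, if ENDS lower toxicant exposure mainly by moving people off cigarettes, comparing quitters with quitters sets that benefit aside by construction.

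No passage says which analysis is the principal one for the toxicology objective. A null or unfavourable result among quitters could therefore be reported under the intention-to-treat label and read as the randomised answer.

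**Working it through.** **Sizes.** Inputs are the 6-month rows of Table 11.2-1.

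- Protocol 2.0 table: Ai+Ci = 59 + 53 = 112; Ac+Cc = 6 + 64 = 70; Ai+Ac = 59 + 6 = 65; Ci+Cc = 53 + 64 = 117. These are the figures still printed in 11.2.
- Protocol 9.0 table: Ai+Ci = 56 + 50 = 106; Ac+Cc = 11 + 56 = 67; Ai+Ac = 56 + 11 = 67; Ci+Cc = 50 + 56 = 106.
- Expected evaluable per arm: 586 − 29 = 557, so 1,114 in all. Quitters: 106 + 67 = 173, or 15.5%.

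**What the contrast leaves out, and what it mixes.**

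- Expected ENDS users in the intervention arm: 56 + 111 = 167. The 111 who still smoke (66%) are dropped.
- ENDS users among quitters: 56/106 = 52.8% in the intervention arm and 11/67 = 16.4% in the control arm, a gap of 36.4 points. If level among quitters depended only on ENDS use, the arm contrast would show about 36% of the vaping v non-vaping difference. The second contrast, Ai+Ac v Ci+Cc, separates by ENDS use but is not by allocation at all.

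**The plan's own power figure.** Table 11.2-2 gives urinary 8-OHdG as 3.62 (SD 2.41) in past smokers and 4.24 (SD 3.3) in current smokers, with correlation 0.7, 112 v 70, power 48% and N = 174 per group. Take two-sided alpha 0.05 and a baseline-adjusted variance factor of 1 − 0.7² = 0.51.

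- Difference = 4.24 − 3.62 = 0.62.
- SE = √[0.51 × (2.41²/112 + 3.3²/70)] = √(0.51 × 0.2074) = 0.325.
- Power = Φ(0.62/0.325 − 1.96) = 47.9%.
- N for 80% power = 0.51 × (2.41² + 3.3²) × (1.96 + 0.842)² / 0.62² = 173.9.

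Both figures reproduce. They do so by giving the past-smoker mean to the 112 and the current-smoker mean to the 70. Yet 112 and 70 are both groups of quitters. The 48% is therefore power for quitters v continuing smokers, as the table's footnote says, at group sizes belonging to a different contrast. With 106 and 67 it is 46.1%.

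**Whole-arm comparison.** Assumptions: markers change only in quitters; quit rates 19% v 12%; current-smoker SD in both arms; correlation 0.7; 557 per arm. The expected arm difference is the past v current difference × 0.07. SE = SD × √0.51 × √(2/557). Power is the chance of a significant result in the expected direction.

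| Urinary marker | Past v current | Arm difference | SD | Power |
|---|---|---|---|---|
| 8-OHdG | 0.62 | 0.043 | 3.3 | about 5% |
| 1-OHP (0.11 v 0.20) | 0.09 | 0.0063 | 0.25 | about 9% |
| 8-isoprostane (0.74 v 1.1) | 0.36 | 0.025 | 0.1 | near 100% |
| 8-isoprostane (0.7 v 4.48, never v current smokers) | 3.78 | 0.265 | 2.7 | 63% |

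Under the same assumptions, and with no selection, the quitters-only contrast has an expected difference of 0 for every row.

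**The case against.** The strongest reply is that the disputed sentence sits in the sample-size section, while the planned-analysis section begins with exactly the arm comparison one would want. Section 11.4.3 and the synopsis place no restriction to quitters, and 11.4.1 applies to all analyses. This stands. A reader of 11.2 alone might infer that the whole toxicology objective hangs on the quitters-only contrast; the documents do not support that. Micronuclei come closest: they are named in 11.2 and missing from the 11.4.3 list, but the general rule in 11.4.1 still covers them.

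The second reply is that comparing quitters is deliberate. The synopsis names exposure in quitters with or without ENDS as a gap in knowledge, section 3.1 discusses that comparison, and 11.2 says toxicology will be compared by ENDS exposure. For that question, setting aside the cessation route is the intention. This also stands, and it is a reason to keep the contrasts. It is not a reason to call either of them intention-to-treat.

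Third, imbalance in dependence or baseline exposure between the quitter groups is a risk created by selection; no figure in the documents shows it. Fourth, which biomarker analysis is principal may be fixed in the separate registrations that the SAP mentions and that are not shown here.

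What none of this removes is the conflict over the label, the outdated counts, and a power statement that does not belong to the contrast beside it.

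**Conclusion.** The point holds in a limited form. Section 11.2 gives the intention-to-treat label to a comparison of 173 expected quitters out of 1,114 evaluable participants, selected on an outcome expected at 19% v 12%. This contradicts 11.4.1 and does not match 11.4.3. The printed sizes (112 v 70, 65 v 117) disagree with the current table (106 v 67, 67 v 106). The 48% power for 8-OHdG describes quitters against continuing smokers and neither quitters-only contrast.

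It would go too far to present the arm differences in the table, against 0 among quitters, as the size of a bias. They assume no change in dual users or continuing smokers, although the plan expects 111 v 17 dual users, whose exposure could move the arm difference either way. The 0 further assumes equal levels in vaping and non-vaping quitters. The figures show that the two analyses estimate different things; they do not forecast results.

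**What to change.** In section 11.2:

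- Name the arm comparison already planned in 11.4.3 as the intention-to-treat analysis of the toxicology objective, and add micronuclei to it. Analyse the 6-month level adjusted for its baseline value, and use the censoring weights of 11.5 for missing samples. State the expected evaluable number: about 557 v 557 for markers collected at all sites, and fewer for micronuclei, which the site table in 9.2 limits to Bern and Lausanne.
- Relabel Ai+Ci v Ac+Cc and Ai+Ac v Ci+Cc as non-randomised, exploratory contrasts of residual exposure among quitters. Adjust them for baseline biomarker, cigarettes per day and dependence, and update their sizes to 106 v 67 and 67 v 106.
- State that the 48% for 8-OHdG is power for quitters v continuing smokers and applies to neither quitters-only contrast.
- Disclose whole-arm power with its assumptions.

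The cost is wording plus one baseline-adjusted regression per marker on data already collected. The drawback is that the randomised comparison will be weak for some markers, about 5% for 8-OHdG and 9% for 1-OHP if only quitters change. A null result there must not be read as absence of effect.
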